3. EQ5D Quality of life questionnaire [Time Frame: Baseline + end point at 12 weeks + follow up at 6 months and 12 months]
4. UCLA Loneliness Scale [Time Frame: Baseline + end point at 12 weeks + follow up at 6 months and 12 months]
5. Self-Efficacy for Exercise [Time Frame: Baseline + end point at 12 weeks + follow up at 6 months and 12 months]
6. Outcome expectancy for Exercise-2 [Time Frame: Baseline + end point at 12 weeks + follow up at 6 months and 12 months]
7. Copenhagen Social Relations Questionnaire [Time Frame: Baseline + end point at 12 weeks + follow up at 6 months and 12 months]

Secondary outcome measures include participant reported outcomes administered by online questionnaires. The baseline measurement will be undertaken before the intervention group receives the first motivational interview and the end point measurement will be undertaken in the days after the last motivational interview.

International Physical Activity Questionnaire short form (IPAQ-SF)

The seven-item IPAQ-SF measure assesses the types of intensity of physical activity and sitting time that people has done the past seven days as part of their daily lives are considered to estimate total physical activity in MET-min/week and time spent sitting [31]. The score is categorized to three levels of (categories) of PA; low, moderate and high [32]. In a review of 16 international studies of

the measurement properties IPAQ-SF showed acceptable reliability (Spearman's rho: 0,32-0,88) [31] and low to moderate concurrent validity against accelerometer had a pooled correlation coefficient of 0.30 (Spearman's rho range: 0,09-0,38) [33]. The Danish version have been used in a Danish population of older adults [34].

Nordic Physical Activity Questionnaire short (NPAQ-short)

The two-item NPAQ-short [35] is a short revised version of the original NPAQ, a survey tool based on telephone interviews designed for assessment of Moderate and Vigorous Physical Activity (MVPA). It is developed to monitor compliance with the WHO recommendations on PA [36] and has showed moderate correlation with objectively measured MVPA (Spearman's rho: 0.33) in a Danish population with an average age of 43 (range: 17-85) [35].

The 5-level EuroQol-5 Domain (EQ-5D-5L) Quality of life questionnaire

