The EQ-5D-5L is a generic health-related quality of life (HRQoL) measure developed as a non-disease-specific instrument for describing and valuing health states [37] and comprises five dimensions (mobility, self-care, usual activities, pain/discomfort and anxiety/depression), each of which has three levels (no problems, moderate problems and extreme problems) and a visual analogue scale (EQ VAS). The score for the five dimensions can be combined into a five-digit number that describes the patient's health state. The EQ VAS records the patient's self-rated health on a vertical visual analogue scale, where the endpoints are labelled 'The best health you can imagine' and 'The worst health you can imagine'. The EQ-5D-5L has shown general feasibility for measuring HRQoL in a geriatric population sample [38] as well as acceptable reliability and validity [39]. The EQ-5D-5L is adapted to Danish [40] and in the national sample of Danish 70-79 year-olds, the mean EQ-5D-5L index score was 0.83 (SD: 0,19) [41].

UCLA Loneliness Scale

The 20-item UCLA loneliness scale (third version) is a self-report measure of loneliness and social isolation [42]. The scale consists of 11 positive and nine negative items and the total score is calculated by finding the sum of 20 items (0-60), with a higher score indicating more loneliness. Items one, five, six, nine, 10, 15, 19 and 20 are all reverse scored. The scale is adapted to Danish and this version has shown high internal consistency (Cronbach's Alpha: 0.92) and has shown evidence of

convergent validity as a moderate to high correlation with other measures of emotional loneliness (r : 0.69) and social loneliness (r : 0.73). In addition, the scale shows evidence of discriminant validity by its relations to self-esteem (r : -0.58), depression (r : 0.59), extraversion (r : 0.57) and neuroticism (r : 0.58). in a population of Danish 8th grade students that are comparable to the original scale [43]. The scale has showed acceptable model fit as a unidimensional structure [43].

Self-Efficacy for Exercise (SEE-DK)

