The nine-item SEE-DK addresses confidence to engage in regular exercise [44], when challenged by known barriers to exercise [4]. The scale was developed initially for sedentary adults in the community who participated in an outpatient exercise program [45] and was revised to older adults [44]. It is designed to be administered using face-to-face interview. Response categories range from 0 (no confidence) to 10 (very confident) [44]. Item scores are used to calculate a total score (0-90), with higher scores indicating higher confidence, or self-efficacy, related to exercise. The SEE-DK is adapted to Danish older adults with acceptable face and content validity, construct validity by acceptable model fit as a unidimensional scale, and test-retest reliability [46].

Outcome Expectancy for Exercise-2 (OEE2-DK)

The 13-item OEE-2 scale was developed from the original 9-item Outcome Expectations for Exercise scale (OEE) that specifically focused on measuring the positive outcome expectations for exercise (POEE). Based on qualitative findings [4, 47], the original OEE was revised to include four items that focused on negative outcome expectations for exercise (NOEE) [48]. It was initially developed for older adults [49, 50]. To complete the OEE2-DK scale the participants are asked, using a Likert scale, to *strongly agree*, *agree*, *neither agree nor disagree*, *disagree*, or *strongly disagree* with the stated outcomes to each statement of exercising. The POEE and NOEE subscales are scored by calculating the average score on each scale (1-5) and the items three, six, nine and 12 (NOEE subscale) are reverse-scored [48]. The OEE2-DK is adapted to Danish older adults with acceptable face and content validity, construct validity by acceptable model fit as a two-dimensional scale, and test-retest reliability [46].

Copenhagen Social Relations Questionnaire (CSRQ)

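### UCLA Loneliness Scale: the eight reverse-scored items listed do not match the stated split of 11 positive and nine negative items

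*Combined protocol and SAP*

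**What the plan says.** The description is in section 12 (Outcomes), under UCLA Loneliness Scale. The instrument is introduced as "The 20-item UCLA loneliness scale (third version) is a self-report measure of loneliness and social isolation". On item direction the plan states: "The scale consists of 11 positive and nine negative items". The total is the sum of the 20 items, with a range of 0 to 60, "with a higher score indicating more loneliness". The scoring rule follows: "Items one, five, six, nine, 10, 15, 19 and 20 are all reverse scored".

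The scale is the fourth of seven secondary outcomes in section 12, measured at baseline, 12 weeks, 6 months and 12 months. Section 20 says that the secondary outcomes get the same analysis as the primary outcome. No other section gives item wording, a scoring key or a further reverse-scored item for this scale.

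**The concern.** A sum score has a clear direction only if every item points the same way once recoded. On a scale with two groups of oppositely directed items, the reverse-scored list should therefore be the whole of one group. Here the groups are said to have 11 and nine members, and the list has eight.

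This is the plan's only scoring instruction for the outcome, so a programmer working from the protocol could code it as it stands. If the list is the faulty sentence, one or more items would be added to the total in the wrong direction, at all four time points. The score level would be distorted, raw differences between the arms would be diluted, and the results would not be comparable with other UCLA data, including the Danish validation data that the plan cites.

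**Working it through.** **Inputs** (all from section 12, UCLA Loneliness Scale): 20 items; split 11 and nine; total 0 to 60; reverse-scored items 1, 5, 6, 9, 10, 15, 19, 20; Cronbach's alpha 0.92 for the Danish version, reported in 8th grade students.

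**1. Figures that reproduce.** 11 + 9 = 20 items. 60/20 = 3, so each item is scored 0 to 3.

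**2. The figure that does not.** The list holds eight distinct items, which equals neither nine nor 11. The plan does not say whether positive refers to wording or to scoring direction, so both readings are needed:

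| Group to be reversed | Items needed | Items listed | Minimum mis-keyed |
|---|---|---|---|
| Nine-item group | 9 | 8 | 9 − 8 = 1 |
| 11-item group | 11 | 8 | 11 − 8 = 3 |

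Both results are minimums. They assume that all eight listed items belong to the right group, which the documents do not show.

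**3. A comparison in the same section.** For OEE2-DK the plan describes four negative-expectation items and then says that "the items three, six, nine and 12 (NOEE subscale) are reverse-scored". Four items are described and four are listed, so there the count and the list agree.

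**4. Error in one person's total, if the split is right.** A mis-keyed item enters as 3 − x instead of x, an error of 3 − 2x, which is +3, +1, −1 or −3 for x = 0, 1, 2, 3. It is never zero. A list of eight differs from a set of nine or 11 by an odd number of items, and an odd number of odd errors cannot sum to zero. So, on this condition, no fully completed questionnaire would give the correct total.

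**5. Raw group difference.** Assume the same true difference d on every item. Correctly keyed, the total differs by 20d. With w items backwards it differs by (20 − 2w)d:
- w = 1: 18d/20d = 90%
- w = 3: 14d/20d = 70%

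**6. Standardised difference.** Assume equal item variances (set to 1) and one common inter-item correlation r. From alpha = 20r/(1 + 19r),

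r = 0.92/(20 − 0.92 × 19) = 0.92/2.52 = 0.365.

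Variance of the total = 20(1 − r) + r(20 − 2w)²:
- w = 0: 12.70 + 146.03 = 158.73
- w = 1: 12.70 + 118.29 = 130.98; SD ratio √(130.98/158.73) = 0.908; standardised ratio 0.90/0.908 = 0.991
- w = 3: 12.70 + 71.56 = 84.25; SD ratio √(84.25/158.73) = 0.729; standardised ratio 0.70/0.729 = 0.961

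Alpha for the mis-keyed total = (20/19)(1 − 20/variance): 0.89 for w = 1 and 0.80 for w = 3, against 0.92.

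**7. Would a data check reveal it?** Under the same assumptions, a backward item's correlation with the sum of the other 19 items is:
- w = 1: −19r/√(19(1 − r) + 19²r) = −6.94/11.99 = −0.58
- w = 3: −15r/√(19(1 − r) + 15²r) = −5.48/9.71 = −0.56

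A mis-keyed item would stand out by its sign.

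**The case against.** The strongest reply is that the documents prove a contradiction, not a scoring error. If the split is the misstatement and the scale has 12 and eight items, the eight-item list may be complete and every total correct. Choosing between the two sentences needs the scoring key in the cited sources, which the documents do not reproduce. This stands, and it is why the consequences are stated conditionally. A reader might infer from the mismatch that loneliness will be mis-scored for every participant; that follows only if the split is the correct sentence.

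Two other stronger readings also fail. A reader might take three as the most items that could be backwards. It is the minimum under the 11-item reading, and without item wording no maximum can be given. A reader might also take the 10% to 30% loss in the raw difference as a comparable loss of power. Power follows the standardised difference, which hardly moves, because the SD shrinks along with the mean difference. The same rule applies to both arms, so nothing in the documents points to a bias in favour of either.

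It is also fair to say that the outcome is peripheral. Loneliness is named in none of the three hypotheses in section 7. If item responses are kept, the score can be recomputed.

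The reply does not remove the contradiction. Eight is neither nine nor 11 under any reading of positive and negative. The sentence is complete and grammatical, so text extraction is an unlikely cause. It is an instruction, not background.

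**Conclusion.** Wrong as written, low severity. The reverse-scored list and the item split contradict each other, and nothing else in the documents reconciles them.

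If the split is correct, at least one item is keyed backwards (nine-item group reversed) or at least three (11-item group reversed). For exactly one or three, the raw difference falls to 90% or 70% and the standardised difference to about 99% or 96%. The raw figures assume an effect spread evenly over items. The standardised figures also assume equal item variances and a common inter-item correlation, derived from an alpha reported in 8th grade students, not in people aged 70 or over. The more tangible harm is to score level and comparability: a person who should score 0 on a mis-keyed item is given 3.

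If the split is misstated and the list is complete, only the description is wrong. The damage is confined to one of seven secondary outcomes; the step-count primary outcome and the sample size are untouched.

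**What to change.** Before the scale is scored and the groups are unblinded:

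1. Compare both sentences with the scoring key of the version and language in use, and correct whichever is wrong. Check the item numbers as well as the count, since a list of the right length could still name the wrong items.
2. State whether positive and negative refer to item wording or to scoring direction.
3. After recoding, using data pooled over the arms, confirm that each of the 20 items correlates positively with the sum of the others. This backs up the key and does not replace it.

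The cost is one corrected line of protocol text, at most one line of scoring code, and a short blinded check. Nothing changes for participants. Doing it before unblinding avoids a change of scoring rule after the results are known.

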The objective of this randomized controlled trial is to investigate if motivational interviewing provided as an add-on intervention to a physical activity intervention will increase the average daily step count in community-dwelling participants above the age of 70.

1. It is hypothesized that motivational interviewing, will enhance the average daily step count among participants.
2. It is hypothesized that motivational interviewing, will affect self-reported physical activity and quality of life.
3. It is hypothesized that self-efficacy and outcome expectancy for exercise, will mediate the effect and explain heterogeneity in the results.

8. Trial design

Study Type: Interventional

Estimated Enrollment: 154 participants

Allocation: Randomized

Intervention Model: Parallel Assignment

12-week intervention with two groups in a parallel design

Masking: Double (Investigator, Outcomes Assessor)

Primary investigator will be blinded for allocation before making the final analyses. No outcome assessments will be made by an assessor. Only objectively measured steps per day and participant reported outcome measures will be used for this study.

Primary Purpose: Prevention

The primary hypothesis will be investigated with a superiority analysis.

Methods: Participants, interventions, and outcomes

9. Study setting

Description of study settings (e.g., community clinic, academic hospital) and list of countries where data will be collected. Reference to where list of study sites can be obtained'.

This RCT will be conducted in Denmark. Participants eligible for inclusion will receive the content necessary for participation by mail. The participants will only have contact with the research team via phone or e-mail correspondence.

10. Eligibility criteria

Participants will be considered eligible for inclusion if they; 1) are retired and community-dwelling, 2) at least 70 years of age by the day of enrolling the trial, 3) own a smartphone or tablet able to install the *Garmin Connect application*, 4) have an email address and are able to correspond and complete the study survey on a computer and 5) have hearing abilities sufficient to receive a telephone interview.

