Participants will not be considered eligible for inclusion, and hence excluded, if; 1) they have cognitive impairment from moderate to severe dementia or Alzheimer's disease, 2) they are undergoing active chemotherapy or palliative care from cancer, 3) have a major mobility impairment (e.g. from paralysis, amputations, severe arthrosis or arthritis, Sclerosis or Parkinson's disease).

11. Interventions

Experimental: Motivational interviewing Experimental content + base intervention
	
Behavioral: Motivational interviews
 
During the 12-week intervention, the participants will receive seven telephone calls from a physical therapist (PT). Using an intervention schedule inspired by the work of King et al. to facilitate initiation and maintenance of behavior change, calls are delivered in week 1, 2, 3,5,7,9, and 12 [29].
 
The telephone call will consist of a motivational interview (MI) focused on enhancing the daily level of physical activity in the participants.
 
MI is a form of counselling aiming at prompting increases in self-efficacy, which may leave people more open to and invested in changing their behaviors and shows potential for significant effects for exercise behavior change. In this person-centered intervention model, participants are guided through self-reflective counseling. They receive feedback on these health behaviors in relation to national recommendations; consistent with a MI approach [27], this feedback also highlights the discrepancy between their health goals and their current health behaviors; they set collaborative goals for physical activity change with their PT, with the participant encouraged to begin with the target area in which she/he is most motivated to change; all of this is incorporated into a behaviorally-specific plan that specifies exactly what is to be done and when; barriers and supports are identified; confidence is assessed and problem-solving is discussed as necessary. These steps are repeated during intervention contacts, with goals being adjusted as necessary.
 
During the maintenance face (week 5-12) increasing emphasis is placed on identification of multi-level supports for health behavior change. Participants are encouraged to use a variety of supports including family and friends, as well as neighborhood and community supports. In collaboration with local community partners, a community reference

---	--

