The 42-items questionnaire was developed originally in Danish in 1999 [51] and measures the structural aspect of social relations, with focus on contact frequency and diversity, and functional aspects with focus on perceived social support. CSRQ has been used in several Danish population-based surveys including in the Copenhagen Aging and Midlife Biobank (CAMB) [52]. In a sample of 38-69 old adults the CSRQ showed acceptable face and content validity and good test-retest reliability by 41% of the items had substantial to almost perfect agreement (kappa: 0.65-0.97) and the rest showed moderate agreement (kappa: 0.41-0.60) [53].

The secondary outcomes will also serve as follow up measurements six and 12 months after ending the intervention. They will also be conducted with online surveys.

13. Participant timeline

Time schedule of enrolment, interventions (including any run-ins and washouts), assessments, and visits for participants. A schematic diagram is highly recommended (see Figure).

[figure not shown]

Figure 1. SPIRIT participant timeline.

14. Sample size

Estimated number of participants needed to achieve study objectives is 128 participants. The number will be enough to show a 0.5 standard deviation difference between groups, equal to a moderate effect size. The number of participants will yield a power on 80% with a significance level on 0.05. To account for attrition this study will include 20% more participants than the above mentioned, and hence terminate the inclusion of participants when 154 participants in total and 77 in each group have been enrolled.

15. Recruitment

We will recruit participants through online advertisements on social media and in non-profit organizations working with older adults. We will also try to recruit participants at activity centers and other communities of older adults.

Methods: Assignment of interventions

16. Allocation

16.a. Sequence generation

Participants will be randomly assigned to either the intervention or the control group, with a 1:1 allocation. Eligible participants who have completed the baseline step count, will be randomized in blocks of four participants or more, stratified on sex (M/F) and average baseline step count for the extracted days prior to the allocation. Randomization of participants will happen every week, except weeks with less than four new participants.

16.b Allocation concealment mechanism

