Participants will be randomized using STATA, which is a statistical software package. Allocation concealment will be ensured, as the allocation will not be available until the patient has been recruited into the trial, which takes place after the baseline step count measurements have been completed.

16.c Implementation

One investigator will be in charge of the randomization. That investigator will receive a list of participant IDs every week and randomize the participants according to the above. That one investigator will not have anything do to with recruitment nor statistical analyses.

17. Blinding (masking)

17. a

Outcome assessors and data-analysts will be blinded for participant allocation.

17b.

Due to the nature of the intervention neither participants nor staff conducting the motivational interview in the intervention group can be blinded to allocation but are strongly inculcated not to disclose the allocation status of the participants with the principal investigator who will conduct the analyses. The group names of the intervention and the control group will be anonymized before the data will be analyzed to ensure blinding of the principal investigator.

Methods: Data collection, management, and analysis

18. Data collection methods

18a. Plans for assessment and collection of outcomes

Primary outcome

The primary outcome (average steps per day in the 12-week intervention period) will be extracted from the data management software Fitrockr. Participants will be asked to synchronize their PAMs and their Garmin Connect application daily, ensuring daily storage of the step counts. The PAMs have a 30-day storage for daily totals so data will not be lost, even if the participants forget to synchronize their PAMs for longer periods of time. Fitrockr will extract the data from Garmin Connect and make daily step counts available for export through their service. When the participant has completed the 12-week intervention, the daily totals will be extracted as 84 variables (12*7). After the data extraction, the average daily step count will be calculated.

Secondary outcomes

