The secondary outcomes are all participant reported and administered through SurveyXact. All participants will receive an email with an electronic SurveyXact invitation on the day of randomization. On the last day of intervention (day 84), the participants will receive a similar SurveyXact invitation with the end-point questionnaire. The six and 12-month follow up assessments will be administered in similar ways to the end-point assessment.

Demographic and other baseline items

Non-outcome variables will be included in the baseline questionnaire.

18b. Plans to promote participant retention and complete follow-up.

If possible, reasons for drop out will be collected from each discontinued participant. The available data on the primary outcome will be used to calculate the intervention period average steps per day. If the participant fails to synchronize the PAM and a possible drop out is suspected, a person from the research team will call the participant to either remind them to synchronize the PAM or try to motivate the participant to continue the intervention.

Lost to follow up with the end-point or follow up questionnaires will be reminded via email 7, 14 and 21 days after the deadline.

19. Data management

All outcomes will be handled and stored electronically.

Steps per day will be stored every time the participant synchronizes the PAM. The data handling responsible Fitrockr will extract data from the Garmin applications and store it according to the agreements. Every time a participant completes the intervention period, their data will be exported from the Fitrockr database and stored securely at the University of Copenhagen server.

During the study, with participants' verbal consent, telephone MI (and control) sessions is audiotaped on a regular basis to ensure fidelity of intervention delivery and to provide counselor feedback.

The participant reported outcomes for the secondary outcomes will be administered using SurveyXact, securing data every time a survey has been completed. Every time a participant completes the intervention period, their data will be exported from the Fitrockr database and stored securely at the University of Copenhagen server.

No personal data will be exported from Fitrockr or SurveyXact without pseudonymization. Complete anonymization of all data will be done after the last follow up period. Data protection agency approval Reference number: 514-0268/18-3000

20. Statistical methods

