The primary outcome will be analyzed as a mixed effects model, where intervention group are analyzed fixed and participants are random effects. The analysis will investigate the group difference in average daily step count, adjusted for baseline step count and gender. Same analysis will be performed on secondary outcomes.

Drop outs with data on the primary outcome for at least one week will have their average daily step count based on the available days. All analysis will be performed following the Intention to Treat (ITT) principle imputing missing data using a multiple imputation based on age, gender, baseline step counts and average daily step count (for missing data on the secondary outcomes). In

calculating the average daily step count, days with less than 100 steps will be handled as “days of non-wear” and excluded assessing the mean step count.

Methods: Monitoring

21. Data monitoring

Not applicable/relevant

22. Harms

In our study an adverse event will be defined as any untoward medical occurrence in a participant without regard to the possibility of a causal relationship with the intervention. Adverse events will be collected after the subject has provided consent and enrolled in the study. If a participant experiences an adverse event after the electronically administered informed consent has been signed (entry) but the subject has not started to receive study intervention, the event will be reported as not related to the intervention. All adverse events occurring after entry into the study will be recorded. The participants will be asked at the end-point questionnaire if they experienced any adverse events in terms of using the PAMs or trying to enhance their daily amount of physical activity.

23. Auditing

No auditing has been protocolled.

Ethics and dissemination

24. Research ethics approval

According to a written correspondence with the Danish Ethics Committee in the Capital Region of Denmark, this trial was not subject to the current laws on research ethics in Denmark due to the non-invasive behavioral change intervention. The study can be conducted without further approval from the Danish Ethics Committee in the Capital Region of Denmark (Journal-nr.:18004960).

25. Protocol amendments

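### The baseline questionnaire goes out on randomisation day and is not stated to be due before participants learn their arm, an avoidable exposure for analyses that use those baselines

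*Combined protocol and SAP*

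**What the plan says.** All seven secondary outcomes are self-reported online, and section 12 lists a baseline for each.

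- **Timing of the questionnaire.** Section 18a: "All participants will receive an email with an electronic SurveyXact invitation on the day of randomization". The sentence does not use the word baseline, but the next one describes a similar invitation for the end-point survey on day 84, so the baseline survey is meant.
- **Condition for randomisation.** Section 16.a: "Eligible participants who have completed the baseline step count, will be randomized in blocks of four participants or more". Section 16.b keeps the allocation unavailable until "the patient has been recruited into the trial, which takes place after the baseline step count measurements have been completed". Neither section mentions the questionnaire. Section 10 requires that a participant be able to complete the survey, not that the baseline survey has been completed.
- **Blinding.** Section 17b: "neither participants nor staff conducting the motivational interview in the intervention group can be blinded to allocation".
- **Deadline.** Section 12: "The baseline measurement will be undertaken before the intervention group receives the first motivational interview". Section 11 puts the first interview in week 1: "calls are delivered in week 1, 2, 3,5,7,9, and 12". No deadline is given for the control group, and the reminders in section 18b cover only the end-point and follow-up questionnaires.
- **Use of the baselines.** Hypothesis 3 in section 7: "It is hypothesized that self-efficacy and outcome expectancy for exercise, will mediate the effect and explain heterogeneity in the results". Section 20 describes the primary model as "adjusted for baseline step count and gender. Same analysis will be performed on secondary outcomes".

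**The concern.** A baseline should be a value that allocation cannot have influenced. The plan secures this for step count, which is complete before randomisation, but does not state it for the questionnaires. An unblinded participant who opens the survey after learning the arm may answer differently. Confidence to exercise is an obvious candidate, because one arm has been told that it will be coached and the other that it will not.

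Two uses are at stake. The first is hypothesis 3, where baseline self-efficacy and outcome expectancy would serve as moderators or as starting values for mediation. The second is any secondary analysis that adjusts for the questionnaire's own baseline or takes change from it. If the arms' baselines have moved apart because of disclosure, such an analysis treats part of the reaction to allocation as a pre-existing difference.

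**Working it through.** **Order of events.** The plan gives no figure on this point, so the check starts with the text.

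1. Before randomisation: baseline step count complete (16.a, 16.b).
2. Day of randomisation: allocation generated (16.a) and questionnaire invitation emailed (18a). The order within the day is not stated.
3. Week 1: first interview, intervention arm only (11). The questionnaire must precede it (12).
4. Time at which participants are told their arm: not stated.

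Nothing in the readable text puts submission of the questionnaire before step 4. For the intervention arm the window closes at step 3. For controls no closing point is given.

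**Which analyses are exposed.** Let the true effect on a follow-up score be τ, in SD units with equal SD at both times. Let disclosure move the observed baseline mean by s_I in the intervention arm and s_C in the control arm, and let r be the within-arm correlation of baseline with follow-up.

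- Questionnaire baseline not in the model (literal section 20): expected estimate τ, bias 0.
- Own baseline as covariate: expected estimate τ − r(s_I − s_C), bias −r(s_I − s_C).
- Change score: bias −(s_I − s_C).

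**Numbers.** The documents give neither the shift nor r. Assume a shift of 0 to 0.2 SD in one arm, in either direction, and r of 0.5 to 0.7.

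| Shift (SD) | r = 0.5 | r = 0.7 | Change score |
|---|---|---|---|
| 0 | 0 | 0 | 0 |
| 0.1 | 0.5 × 0.1 = 0.05 | 0.7 × 0.1 = 0.07 | 0.1 |
| 0.2 | 0.5 × 0.2 = 0.10 | 0.7 × 0.2 = 0.14 | 0.2 |

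Entries are absolute bias in SD. On a scale where higher is better, a raised intervention-arm baseline biases against the intervention and a lowered one favours it. A shift in the control arm reverses these signs.

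The shifts are arm means. If only half of an arm answers after disclosure, each late responder must move by 0.1/0.5 = 0.2 to 0.2/0.5 = 0.4 SD to produce them. If a quarter does, the figures are 0.1/0.25 = 0.4 to 0.2/0.25 = 0.8 SD.

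**Hypothesis 3.** The group effect on a mediator adjusted for its own baseline carries the same bias, −r(s_I − s_C). For effect modification of step count no figure can be given, because the documents state no correlation between self-efficacy and steps.

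**The case against.** The strongest reply is that no analysis the plan specifies is shown to be harmed. Section 20 names no own-baseline covariate, change score, moderator model or mediation model. Hypothesis 3 is stated without a method. This stands, and it limits the weight of the point. It does not remove it: hypothesis 3 is a stated aim, studying heterogeneity by self-efficacy needs a baseline value, and a reader could take the instruction to repeat the primary analysis as adjustment for each outcome's own baseline.

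Second, a reader might infer from section 16.b that participants know their arm before they answer. The text does not support that. It says when allocation cannot yet be available, not when anyone is told. Nor does any section say that the questionnaire is optional before randomisation; that is inferred from its absence where the step count is named.

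Third, both arms receive the same base intervention, and no notice of allocation before the first call is described. If the intervention arm learns its allocation at that call, the section 12 rule already places its baseline before disclosure. This is a possible reading but is not stated, and it leaves controls without a limit.

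Fourth, the participant timeline (Figure 1) is not available and could settle the order within randomisation day. It could not place the invitation on an earlier day without contradicting section 18a.

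Last, one might conclude that a baseline given after disclosure can never be repaired. For treatment contrasts that goes too far, since leaving the questionnaire baseline out removes the bias. For a moderator it is true, because the baseline is itself the variable under study.

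**Conclusion.** The point holds as an avoidable exposure, of minor priority. The readable text sends the baseline questionnaire on randomisation day, does not require it before randomisation or disclosure, and sets a limit for one arm only.

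It does not show that any baseline was or will be biased. It does not touch the primary outcome, whose baseline precedes randomisation, or secondary contrasts adjusted only for baseline step count and gender. A reader might infer a threat to the trial's main result; the documents do not support that.

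Where a questionnaire's own baseline is used as covariate, the illustrative bias is 0.05 to 0.14 SD for a shift of 0.1 to 0.2 SD, and zero if there is no shift. The size rests wholly on the assumed shift and on r of 0.5 to 0.7, and the direction is unknown. It should not be read as a share of the 0.5 SD in section 14, which is not tied to any questionnaire. The main reason to act is hypothesis 3: a moderator measured after disclosure cannot be recovered by changing the model.

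**What to change.** - **Section 18a:** send the baseline questionnaire during the baseline step-count period instead of on randomisation day.
- **Section 16.a:** require its submission, as well as the completed step count, for every participant before the ID goes on the weekly list described in section 16.c.
- **Minimum alternative:** keep the invitation on randomisation day, state that no participant in either arm is told the allocation until the questionnaire is submitted, and record the times of submission and disclosure.
- **Section 20:** state whether any secondary or hypothesis 3 analysis uses a questionnaire baseline. If order cannot be assured, leave that baseline out of the treatment contrasts.

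The cost is one email sent earlier and one condition added to an existing list. Consent already runs through SurveyXact (section 26), so no new system is needed. Enrolment would be slightly slower, and those who do not complete the questionnaire would not be randomised. The gap before the intervention starts would lengthen somewhat, more so when a weekly randomisation is skipped for having fewer than four new participants. That matters a little for the seven-day recall of the IPAQ-SF. The minimum alternative does not make randomisation depend on the questionnaire, but it can delay the start for late responders.
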